Large Elastic Artery Stiffness and Compliance: Aortic PWV, the gold standard measurement of large elastic artery stiffness, will be determined using the SphygmoCor device at baseline and 3 months.⁴⁹ Measurement of pulse wave analysis: The cuff of the SphygmoCor device will be placed on the non-dominant arm. BP will be measured involving an automatic recording of brachial BP immediately followed by reinflation of the cuff. The cuff is held at inflation for a period of 5 seconds during which time volumetric waveforms are recorded. Measurement of aPWV: Briefly, a transcutaneous custom tonometer will be positioned at the carotid artery and a cuff will be placed at the femoral artery to measure PWV. The distance between the carotid and the femoral cuff are measured as is the distance between the femoral artery and the femoral cuff. These distances are entered into the SphygmoCor software to determine the carotid-femoral distance used for calculation of PWV.⁴⁹ The tonometer is positioned over the marked location with the strongest carotid pulse detected by the operator. The device automatically captures the pulse wave recording and will be attempted for a full cuff inflation/deflation cycle, plus the first 20 s of the second cuff inflation. SphygmoCor software will perform the velocity calculation.⁴⁹

Laboratory Measurements:

- a) **Plasma comprehensive metabolic panel (CMP):** A CMP will be performed by the University of Colorado Hospital Clinical laboratory at UC-AMC using standard procedures at baseline and 3 months.
- b) **Urinary sCD163:** Urinary sCD163 levels will be assayed using Human CD163 DuoSet ELISA kit in [name] lab as has been previously described.⁵⁰
- c) **Urinary MCP-1:** Urinary MCP-1 will be measured using the R&D Systems Human CCL2/MCP-1 Quantikine ELISA kit as has been previously described.⁵¹
- d) **Plasma TNFR-1:** Plasma TNFR-1 will be measured using Human TNFR1/TNFRSF1A Quantikine ELISA kit as has been described.⁵²

e) **Urinary LTE₄:** After lipid extraction from urine samples, urinary LTE₄ will be measured by liquid chromatography/mass spectrometry.

Justification for secondary outcomes: Vascular endothelial dysfunction and arterial stiffness are key pathophysiological antecedents to CVD in patients with CKD.^{53,54} EndoPat is a common, non-invasive technique used to assess vascular endothelial function. Aortic PWV is the gold standard measurement of arterial stiffness and is non-invasive. [name], MPI and the University of Colorado investigative team have expertise in these vascular function measurements.^{42,55} 3) Increased inflammation may play a critical role in leukotriene activation and subsequent kidney and vascular dysfunction. The effect of montelukast on urinary markers of inflammation and macrophage activation and endovascular markers of inflammation has not been evaluated. Plasma levels of TNFR-1 (a biomarker of systemic inflammation) exhibit a robust association with CKD progression in a variety of patient populations, including those with diabetic kidney disease and hypertensive nephrosclerosis.^{56,57} Urinary MCP-1, a biomarker of systemic and renal inflammation, is also strongly associated with CKD progression in patients with acute kidney injury and hypertension.^{58,59} Although there are limited non-invasive methods to measure macrophage number within kidneys; urinary soluble CD163 has been shown to correlate well with inflammation on renal biopsies.^{50,60} Since LTC₄ and LTD₄ are rapidly metabolized to LTE₄, urinary LTE₄ measurements are a very sensitive and specific way to measure changes in total body cysteinyl leukotrienes.⁶¹ [name], MPI has experience with these laboratory measurements.

Data Management: Data will be collected and managed using Research Electronic Data Capture (REDCap), a secure web application designed to support data capture for research studies. The database is hosted at the University of Colorado Development and Informatics Service Center (DISC), which will be used as a central location for data processing and management. Data quality checks will be ongoing, but will formally occur (e.g., missing data, duplicate entries) at least annually when progress reports are prepared. Blood and urine samples that are not assayed immediately will be stored for later analysis in locked -80° freezers managed by the PI and study staff. All samples will be labeled with the least amount of information necessary to accurately identify the samples (e.g., study number, subject identification number, visit date, and test time-point). Participants who drop from the study may request destruction of samples.

Power Calculations: The goal of this pilot study is to provide parameters to allow for a more accurate estimation of sample size for a larger clinical trial. Our sample size was determined based on feasibility and availability, not a specified statistical power.

Statistical Analysis: Descriptive statistics will be calculated for all variables. For example, mean and standard deviation will be calculated for a continuous variable, and count and proportion will be provided for a categorical or ordinal variable. For a continuous variable that is not normally distributed, median and interquartile range will be provided, and natural log transformation will be performed before further analysis. The 95% confidence interval will be calculated as well if appropriate.

For the primary outcome 24-hour albuminuria, its log value will be used in analysis. Analysis with a linear regression model will be performed to assess the montelukast effect

by regressing the albuminuria at end of study on baseline albuminuria. Furthermore, analysis with adjustment for age, sex will be performed. For the secondary outcomes for the linear regression model also is applicable, and the same analysis will be performed.

Potential Problems and Alternative Strategies

- Although subject recruitment and retention are always challenging, we should be able to complete the study in the proposed timeline given our group's excellent track record in recruiting, enrolling and retaining participants in clinical trials. The investigative team has access to over 4,000 patients in the CKD clinics at the University of Colorado and the Denver Health Medical Center.
- We should have few difficulties with the proposed experimental procedures and protocols as they are already established in [name] vascular laboratories and [name] laboratory at the UC-AMC. The investigative team has extensive experience with the proposed study measurements.
- Systolic BP is an important determinant of proteinuria and endothelial function and could be a theoretical confounder when interpreting the mechanisms by which montelukast improves proteinuria and vascular function. All participants must have their BP controlled prior to entering the study.
- We recognize that ACEi/ARB reduce proteinuria and kidney disease progression in patients with CKD. It is possible montelukast has a synergistic effect with these medications. Participants must be on an ACEi/ARB to participate in the study.
- We acknowledge there are other markers of inflammation and it possible that urinary CD163 levels are low in our patient population. Additionally, we acknowledge that measurement of leukotrienes and other inflammatory cytokines in the blood may also be important. For this reason, we are creating a biobank and blood obtained at visits will be stored for future research purposes.

Potential Benefits of the Proposed Research to the Subjects and Others:

Participants will receive benefits associated with overall knowledge of their health from the extensive testing performed for screening purposes and the established subject characteristics (i.e. blood pressure, blood chemistries, etc.). The findings we will generate will answer important questions about montelukast administration in patients with DKD and help investigators design future clinical trials in this population. Thus, the new knowledge generated from this proposal will yield potential benefit to DKD patients in general and to society as a whole.

4. Importance of the Knowledge to be Gained: The new knowledge generated from this proposal will facilitate planning of future clinical trials in DKD patients that will aim to reduce the morbidity and mortality of DKD.

H. References:

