Our earlier studies have shown that macrophages promote tubular damage and renal fibrosis through activation of the **5-lipoxygenase (5-LO) pathway**. The 5-LO pathway is responsible for the synthesis of pro-inflammatory lipid mediators, known as leukotrienes. Leukotrienes have been implicated in the etiology of CKD and CVD. We showed that leukotrienes promote chronic inflammation and maladaptive renal tubular repair in several mouse models of renal fibrosis. We have recently found that short term inhibition of cysteinyl leukotrienes with montelukast (a leukotriene antagonist) in mice with acute kidney injury potently prevents CKD. This is associated with decreased chronic inflammation and improved tubulointerstitial repair. Leukotrienes also cause endothelial dysfunction which increases glomerular permeability to albumin and causes vascular dysfunction leading to CVD. Short-term treatment with a 5-LO inhibitor reduces proteinuria in patients with glomerulonephritis. Additionally, montelukast use is associated with reduced cardiovascular events in the general population. **However, to date, no interventional studies have examined the effect of montelukast on kidney or cardiovascular outcomes in patients with DKD.** Montelukast is currently used for asthma treatment and has an excellent safety profile for long-term use in both pediatric and adult patients, making it an attractive and safe option for chronic therapy in patients with DKD.

Our overall hypothesis is that cysteinyl leukotrienes promote DKD progression and vascular disease by increasing inflammation, tubular damage, endothelial dysfunction and

fibrosis. We will conduct a prospective, open-label pilot clinical trial examining the effect of oral montelukast for 3 months in 20 patients with DKD (eGFR 30-59 ml/min/1.73m²) with urine albumin to creatinine ratio of 200-5000 mg/g and use of a RAAS inhibitor (may also be on stable dose of SGLT2i) to test the following aims:

Hypothesis 1: Treatment with montelukast will reduce proteinuria in patients with DKD.

Specific Aim One: To determine changes in 24-hour urine proteinuria before and after 3 months of montelukast therapy.

Hypothesis 2: Treatment with montelukast will improve vascular endothelial function and arterial stiffness in patients with DKD.

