
 • Age 30-70 years • Urine albumin to creatinine ratio 200-5000 mg/g on first morning void • CKD stage 3 at time of screening (eGFR 30-59 ml/min/1.73m²) • Blood pressure <140/90 mm Hg prior to baseline visit • Use of angiotensin converting enzyme inhibitor or angiotensin receptor blocker or mineralocorticoid receptor antagonist with stable dose for 4 weeks • History of diabetes type 1 or type 2 • BMI < 40 kg/m² (FMD measurements can be inaccurate in severely obese patients). • Stable anti-hypertensive regimen for at least one month prior to enrollment • Stable diabetes regimen for at least one month prior to enrollment • Sedentary or recreationally active (<2 days of vigorous aerobic exercise as vigorous exercise may affect vascular function measurements) • Able to provide consent 	
 • Significant comorbid conditions that lead the investigator to conclude that life expectancy is less than 1 year • Uncontrolled hypertension • Factors judged to limit adherence to interventions (e.g. history of medication noncompliance, noncompliance with follow up visits, significant cognitive impairment, etc.) • Anticipated initiation of dialysis or kidney transplantation within 3 months • Current participation in another research study • Pregnancy or planning to become pregnant or currently breastfeeding • Allergy to aspirin • Severe hepatic impairment (Child-Pugh Class C) • History of major psychiatric disorder • Use of inhaled or systemic corticosteroids or long-acting beta agonists (higher risk of neuropsychiatric reaction) • Current use of phenobarbital, rifampin or carbamazepine.

Rigorous Experimental Design. A 3-month **open-label, prospective pilot study** with oral montelukast will be conducted. The study will include 3 phases: screening, baseline, and follow-up.

- **Screening:** Subjects will undergo screening for inclusion/exclusion criteria during a 1-2 week period. Participants will have urine albumin/creatinine performed and basic metabolic panel to determine eligibility.
- **Baseline:** During the baseline phase the following will be measured: 1) 24-hour albuminuria; 2) vascular function (EndoPat, aPWV); 2) serum chemistry panel; 3) urine MCP-1, sCD163 and LTE₄; and 4) plasma TNFR-1.

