- **Follow-up:** The follow-up schedule includes assessments at 3 months with monthly safety visits (either via phone, in person, or survey link). An additional safety check will be performed via phone, in person, or survey link 2 weeks after the last study visit.

Study Drug Dosing: Study drug will be received from the University of Colorado Hospital Pharmacy. Each bottle will contain 90 tablets of montelukast 10mg. Participants will receive 1 tablet daily (10mg) for the entire 3 months. The tablet will be taken in the evening per manufacturer recommendations. The dose of montelukast may be adjusted.

Rationale for study duration: From the study team's experience with other interventional studies evaluating albuminuria and vascular endothelial function changes can be seen in 4-6 weeks. Changes in aPWV can be seen after 12 weeks. Changes in patients with CKD stage 3 may require longer periods of time for these endpoints and published data use a period of 3-6 months.^{42,44} Hence, we are proposing a 3-month intervention for this pilot study.

Data Collection

- Demographics, medical history and physical examination will be performed at screening or baseline visit.
- **Circulating measures:** Subjects will report fasted for standard blood chemistry analysis at baseline and 3 months. A urine pregnancy test will be performed if clinically indicated at the screening visit.
- **Outcome measures:**
 - 24-hour albuminuria will be measured at baseline and 3 months
 - EndoPat and aPWV will be measured at baseline and 3 months.
 - Urinary LTE₄, MCP-1, and CD163 will be measured at baseline and 3 months.
 - Plasma TNFR-1 and basic metabolic panel will be measured at baseline and 3 months.
- **Resting BP:** Arterial BP will be measured in triplicate while seated at rest using an automated oscillometric machine (Dinamap) at all in-person study visits.
- **Measures of adherence and safety:**
 - Pill counts will be assessed at the 3-month visit to document subject adherence.

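### Date and time-point on sample labels would show assay staff which biomarker samples are on drug, and no masking or re-run rule is stated for the research assays

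*Combined protocol and SAP*

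**What the plan says.** The Data Management section sets one labelling rule: "All samples will be labeled with the least amount of information necessary to accurately identify the samples". Its examples of that information are "e.g., study number, subject identification number, visit date, and test time-point". Samples not assayed at once are "stored for later analysis in locked -80° freezers managed by the PI and study staff".

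The Specific Aims section describes a "prospective, open-label pilot clinical trial examining the effect of oral montelukast for 3 months in 20 patients with DKD", and Rigorous Experimental Design again calls it an "open-label, prospective pilot study". There is one arm. Under Study Drug Dosing, "Participants will receive 1 tablet daily (10mg) for the entire 3 months". Under Data Collection, "Urinary LTE₄, MCP-1, and CD163 will be measured at baseline and 3 months", and plasma TNFR-1 has the same two time-points.

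Laboratory Measurements names a kit or method for each biomarker: ELISA for sCD163, MCP-1 and TNFR-1, and liquid chromatography/mass spectrometry for LTE₄. Only sCD163 is placed in a particular research laboratory ("Urinary sCD163 levels will be assayed using Human CD163 DuoSet ELISA kit in", followed by a name removed from the public copy). The metabolic panel goes to the hospital clinical laboratory.

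**The concern.** In a one-arm before-after study, the time-point of a sample is its treatment status. ELISA and mass spectrometry are instrument readings, but they leave some steps to judgement: which replicate to reject, which sample to dilute or repeat, and how a curve is fitted or a peak integrated. Hypothesis 3 is directional, since it predicts less kidney and vascular inflammation on drug. A reader who knows the time-point therefore also knows the hoped-for result.

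A directional error of this kind goes straight into the before-after change. There is no control arm in which the same error would occur and cancel. It is also separate from plate or kit-lot effects: it would remain even if both samples of a pair were run on one plate. At stake are the Aim 3 markers (sCD163, MCP-1, TNFR-1). LTE₄ is measured under the same conditions, although Aim 3 states no hoped-for direction for it. The protocol says that reduced intrarenal inflammation would support further study in inflammatory subgroups, so these results have a use beyond description.

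**Working it through.** **1. Does the label reveal treatment?** Baseline precedes the drug, and the 3-month sample follows daily dosing throughout. With one arm and two time-points, time-point and treatment status are the same thing. The visit date alone is enough, because the later of a participant's two samples is the on-drug one. Removing the time-point but keeping the date would not mask the assay.

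**2. Is there a safeguard elsewhere?** I looked through Laboratory Measurements, Data Management, Statistical Analysis, and Potential Problems and Alternative Strategies. None describes coded or masked assay, running a participant's two samples together, duplicate readings, a limit on the coefficient of variation (CV), or rules for repeating or rejecting a result.

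**3. How large could the effect be?** The plan has no figure to reproduce: it states no power, effect size, SD or assay error. What follows is an illustration on assumed inputs.

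- Model, log scale, no true mean drug effect: baseline reading b = e₀; 3-month reading f₁ = d + e₁; repeat of the 3-month sample f₂ = d + e₂. Here d is normal with mean 0 and SD 0.20–0.50 (assumed), and each e is normal with mean 0 and assay SD 0.05–0.20 (assumed).
- Assumed unmasked rule: if f₁ > b, re-run and keep the lower of f₁ and f₂. With no effect, this flags half of the 3-month values by symmetry.
- Test: paired t-test on log change, counting significant falls only (nominal 2.5%). The plan itself regresses the end value on baseline; the paired test is a simpler stand-in.
- n = 20 (planned), or 20 × 0.90 = 18, using the 10% attrition that the protocol reports for an earlier vitamin D trial. 40,000 runs per setting.

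| Assay SD (log) | Spurious mean fall | Chance of a false significant fall |
|---|---|---|
| 0.05 | 1.5–1.7% | 3.4–5.5% |
| 0.10 | 3.1–3.6% | 4.5–10.6% |
| 0.20 | 6.8–7.7% | 7.9–21.1% |

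Each range covers both values of n and the assumed SDs of d.

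**4. Check by hand.** The lower of two readings of one sample lies on average SD/√π = 0.564 × SD below the true value. If half of the samples were re-run without regard to their error, the mean log shift would be 0.5 × 0.564 × SD = 0.282 × SD. The fall is 1 − exp(−0.282 × SD): 1.4% at 0.05, 2.8% at 0.10 and 5.5% at 0.20. The simulated values are somewhat larger, as expected, because a 3-month value above baseline more often carries a positive error. On the log scale the shift is proportional to the share of flagged samples actually re-run: at half that share, 3.1–3.6% becomes about 1.6–1.8%.

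**5. When repeats do not depend on time-point or result.** Simulated as two readings averaged for every 3-month sample, the spurious change is −0.13% to +0.06%, and false significant falls occur in 2.3–2.7% of runs.

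**The case against.** The strongest reply is that the label sentence is a privacy rule on minimal identifiers, introduced as an example. It is not an assay procedure. It does not say what the analyst sees at the bench or on the plate map, and recoding before assay would be compatible with it. That stands: a reader might infer that assay staff will see before versus after, but the documents support only that they would if they work from these labels. Recoding is possible but not planned in the text.

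A reader might also infer that all four assays are run by the investigators. Only sCD163 is placed in a named laboratory, and the documents do not say who runs MCP-1, TNFR-1 or LTE₄.

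Nor does the label content contradict the protocol's own minimal-information principle. Each participant gives two sets of samples, and something must tell them apart. A random code linked to a key would do so without revealing the visit, but that is an improvement, not the correction of an inconsistency.

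Finally, discretion in instrument assays is limited, these are not primary outcomes, and the pilot's stated goal is to supply parameters for sizing a larger trial. All of this lowers the priority. It does not supply the missing masking or re-run rule.

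**Conclusion.** The point holds as a cheap improvement. The label content, the equivalence of time-point and treatment, and the absence of masking and re-run rules all come from the text. The size does not. Nothing in the documents shows that selective repeating will happen, and the figures above rest on assumed SDs and a deliberately harsh rule. At an assay SD of 0.10 or less, that rule produces a fall of under 4%; it nears 8% only at 0.20. The real effect is unknown and likely small.

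A reader might extend the point to the primary outcome. The documents do not support that: the laboratory for 24-hour albuminuria is not named, and the metabolic panel goes to the hospital laboratory. It should not be extended to the EndoPat and SphygmoCor results either, because the device software makes those calculations and coding exported files would not mask the operator who acquires the recording. Masking the assays also leaves untouched the larger limitation, the lack of a control arm. It removes one avoidable source of bias in the Aim 3 markers.

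**What to change.** Add a short paragraph to Laboratory Measurements, limited to urinary sCD163, MCP-1 and LTE₄ and plasma TNFR-1:

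- Before assay, relabel the aliquots with random codes, two per participant in random order and showing neither date nor time-point. Someone who does not run the assays should do this.
- Run both samples of a participant on the same plate or in the same batch.
- Keep the code-to-visit key in REDCap, with access withheld from assay staff until the results are locked.
- State in advance the duplicate readings, the CV limit and the rules for repeating or rejecting a result, and apply them without knowledge of time-point.

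Collection labels can stay as they are; clinical chemistry and biobank samples need no change. The cost is a label template, a restricted REDCap field and a short laboratory procedure. No visits or participants are added; the only extra assay work is any duplicate readings not already routine. The downside is a small risk of sample mix-up, which the key controls.

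### The single-arm primary regression of final on baseline log albuminuria has no coefficient equal to the before-after change in Aim 1, and the analysis plan does not name that change, its CI or its SD

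*Combined protocol and SAP*

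**What the plan says.** Section I describes one arm: "We will conduct a prospective, open-label pilot clinical trial examining the effect of oral montelukast for 3 months in 20 patients with DKD". Study Drug Dosing in section IV puts every participant on montelukast, and no comparator is described. Specific Aims 1, 2 and 3 each ask for values before and after 3 months of treatment.

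The Statistical Analysis part of section IV then gives the only inferential method:

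- Scale: "For the primary outcome 24-hour albuminuria, its log value will be used in analysis".
- Purpose: "Analysis with a linear regression model will be performed to assess the montelukast effect".
- Model: "by regressing the albuminuria at end of study on baseline albuminuria".
- Covariates: "Furthermore, analysis with adjustment for age, sex will be performed".
- Secondary outcomes: "For the secondary outcomes for the linear regression model also is applicable, and the same analysis will be performed".

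The other outputs are general. For descriptive statistics, "mean and standard deviation will be calculated for a continuous variable"; for intervals, "The 95% confidence interval will be calculated as well if appropriate". The section does not say which coefficient, contrast or test is the effect, does not define a change variable, and does not say whether baseline, age or sex will be centred. No unit is given for 24-hour albuminuria. Under Power Calculations, the stated goal is to supply parameters for sizing a larger trial.

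**The concern.** The model has the form of a two-arm analysis of covariance with the arm term missing. In a randomised trial the arm coefficient carries the treatment effect. Here no such coefficient exists, and the two that remain, slope and intercept, answer other questions.

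An analyst who follows the text literally would print a slope, almost always highly significant, and an intercept whose value depends on whether albumin is recorded in mg or g. Neither answers Aim 1. Whatever is then reported as the effect would be chosen after the data are seen. The same gap passes to every secondary outcome analysed this way; for an untransformed outcome, the uncentred intercept is the prediction at a baseline of zero.

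The label is a second problem. Without a control, the 3-month change also contains time trend and regression to the mean, and participants are selected on a screening albumin-to-creatinine ratio of 200–5000 mg/g.

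**Working it through.** The plan gives no power, effect size or SD to reproduce; the sample size rests on feasibility. The check is therefore algebra first, then a simulation for scale.

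**Algebra (no assumed values needed).** Let Y0 and Y1 be 24-hour albuminuria at baseline and 3 months, and fit ln Y1 = a + b·ln Y0.

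- A uniform proportional effect shifts every ln Y1 by the same amount, so b does not move.
- a is the fitted ln Y1 when ln Y0 = 0, that is, at a baseline of 1 mg or 1 g depending on the unit.
- Least squares passes through the means, so mean change = a + (b − 1) × mean(ln Y0).
- The covariance of the two visits is b·s0², so variance of change = s1² + s0² − 2·b·s0², where s0 and s1 are the log-scale SDs at the two visits.

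*Worked example.* Take a geometric mean baseline of 1000 mg/day, b = 0.8 and a true 30% fall.

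- In mg/day: a = ln 700 − 0.8 × ln 1000 = 6.551 − 5.526 = 1.025. Change = 1.025 − 0.2 × 6.908 = −0.357, a ratio of 0.70.
- In g/day: a = ln 0.7 − 0.8 × ln 1 = −0.357. Here the intercept equals the change, but only because the centre is exactly 1 g.
- With a centre of 2000 mg/day and no change, a in g/day is 0.2 × ln 2 = 0.139, not 0. Stating the unit alone does not repair the model.

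**Simulation inputs.**

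- n = 18: 20 less roughly the 10–11% attrition reported for the team's earlier trials under Preliminary Data.
- Log SD 0.93 at both visits (assumption): a uniform spread on the log scale over 200–5000 gives ln(25)/√12 = 3.219/3.464 = 0.93.
- Correlation 0.7 / 0.8 / 0.9 (assumption).
- 24-hour centre 500, 1000 or 2000 mg/day (assumption).
- Bivariate normal logs, 20,000 trials per scenario.

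**Share of trials rejecting zero at the two-sided 5% level (r = 0.7 / 0.8 / 0.9).**

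| Quantity tested | No change | True 30% fall |
|---|---|---|
| Slope | 93% / 99% / 100% | 93% / 99% / 100% |
| Intercept, mg/day | 36% / 25% / 14–15% | 25–27% / 15–16% / 7–8% |
| Intercept, g/day, centre 500 | 17% / 12% / 8–9% | 74% / 77% / 88% |
| Intercept, g/day, centre 1000 | 5% / 5% / 5% | 54% / 69% / 92% |
| Intercept, g/day, centre 2000 | 17% / 12% / 8–9% | 11% / 24% / 60% |
| Paired t on log change, any unit or centre | about 5% | 51% / 68% / 93% |

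The mg/day intercept rejects less often when there is a real fall than when there is none. In every simulated trial the two identities above held to within 1e-14. With n = 20 the pattern is the same (paired-t power 55–56% / 73% / 95%).

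**Age- and sex-adjusted model entered uncentred** (5,000 trials per scenario, age uniform 30–70, sex 50/50, 30% fall). The g/day intercept rejects in 10% / 11% / 13% (centre 500), 8% / 9% / 11% (1000) and 5% / 6% / 10% (2000). With change as the response and baseline, age and sex centred, the intercept equals the mean change to rounding.

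**What the named estimate would give.** SD of change = 0.93 × √(2(1 − r)) = 0.72 / 0.59 / 0.42. At n = 18 the half-width is 2.110 × SD/√18 = 0.36 / 0.29 / 0.21 log units. An observed 30% fall would then have a 95% CI of −51% to 0%, −48% to −6%, or −43% to −14%.

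**The case against.** The strongest reply is that every one-arm model lacks a treatment term, including a paired t-test, so the real fault is only an unnamed contrast. Nothing is lost: the change and its SD can be recovered from the fit and the log-scale visit summaries, and the residual SD already serves a baseline-adjusted larger trial. Aim 1 itself names change, and a generous reader could extend the general sentences on descriptive statistics and intervals to cover it. The plan also does not say to test the slope or intercept, sets no alpha and claims no power, so the rejection rates describe a misreading, not a planned decision.

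Much of this stands. The fault is an unnamed contrast, and the simulation only illustrates it. Its figures depend on an assumed SD: at n = 18 and centre 1000, paired-t power is 63% / 80% / 98% with log SD 0.8 and 87% / 96% / 100% with 0.6. The slope is uninformative only for a uniform proportional effect. If the proportional fall grew with baseline the slope would move, but one arm could not separate that from regression to the mean. The paired t's 5% error refers to zero net change, not to a drug effect, and selection at screening was not simulated.

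What does not stand is that the plan already covers the point. No change variable is defined, an interval that is conditional on being appropriate is attached to no quantity, log-scale visit summaries are not expressly promised, and the two visit SDs do not give the SD of change without the slope or correlation. Being recoverable is not the same as being prespecified.

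**Conclusion.** The concern holds. The stated primary analysis, followed as written, prints a slope and an intercept that do not answer Aim 1, and the quantity that does is not named in the analysis section. This follows from algebra and the single-arm design and does not rest on any assumed SD, correlation or centre. The rejection rates do rest on those assumptions and show only what could happen if a printed coefficient were taken as the effect.

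It must be fixed before analysis, because it affects the only inferential model in the plan and carries over to the secondary outcomes. The loss is one of specification, not of data. Even once corrected, the estimate is a before-after change and cannot be attributed to montelukast alone.

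**What to change.** Revise the Statistical Analysis wording as follows.

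1. Make the primary estimate the mean within-participant change in ln(24-hour albuminuria), with a paired-t 95% CI, back-transformed to a percent change. Do the same for each continuous secondary outcome on its analysis scale.
2. If the regression is kept, use change as the response and mean-centre baseline, age and sex. Report the intercept with its CI as the mean change, and do not interpret the slope as an effect. Note that its type I error is slightly raised (about 7% / 6% / 5.5% at n = 18), because the fit treats the sample mean baseline as fixed. Either this or the paired analysis is acceptable; what matters is that one is named.
3. Report the SD of log change and the residual SD, each with a 95% CI, for planning the larger trial. At n = 18 these intervals run from 0.75 to 1.50 and from 0.74 to 1.52 times the estimate.
4. State the unit of 24-hour albuminuria.
5. Describe the result as the change over 3 months on montelukast, and say that time trend and regression to the mean cannot be separated from it.

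The minimum version is one sentence naming the contrast and its CI, plus the SDs to be reported. The cost is wording only, with no new data, visits or participants.
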